3.3.2.2. IA at the end of Open-label Phase

The IA at the end of the open-label phase of the study is planned when all participants have reached:

- Week 144 (Arm 1) and Week 148 (Arm 2), that is, end of treatment [EOT], or discontinued earlier.

Additional IAs may be performed by the sponsor in the open-label phase, given the long duration of the study and the uncertainty of the exact timing of future interactions with health authorities relative to the actual completion of enrollment and time of execution of the primary efficacy analysis.

3.3.3. Rule to Start Part 2 of the Study or Determine Futility

The SC will be unblinded to treatment allocation in the exploration of antiviral activity criteria in Part 1 based on aggregate interim data of HDV RNA and HBsAg, as well as individual HDV RNA and HBsAg profiles. This is to assess whether the initial and early evaluation of antiviral activity warrants the enrollment of participants beyond the subjects in Part 1.

Due to the higher than expected rate of ALT elevations observed during the double-blind treatment phase among several participants in Part 1, the Sponsor has amended the protocol to introduce Part 1 IAs to allow a better characterization of the acute ALT elevations. Hence, the SC decision to initiate Part 2 will not be made before the review of the results of Part 1 IA1, which will include unblinded safety and virology activity data.

However, as soon as Part 2 commences, the SC and Sponsor personnel will be blinded to all Part 2 data. Study site personnel, investigators and participants will have no access to any of the HDV RNA and HBsAg evaluations performed by the IDMC at any time during Part 2.

The SC will use the rule described below to decide whether antiviral activity can be declared, as well as to declare futility if Step 4 is reached. The decision outcome will depend on the timing when the rule is met or not, and after the evaluation of the results of Part 1 IA1.

Antiviral activity criteria to start Part 2

At least 8 participants in Arm 1 have:

- a On-treatment HDV RNA reduction from baseline at any time $\geq 0.5 \log_{10}$ **and**
- b On-treatment HBsAg reduction from baseline at any time $\geq 0.5 \log_{10}$ **and**
- c (≥ 4 participants have on-treatment HDV RNA reduction from baseline at any time $\geq 1 \log_{10}$) **or** (≥ 4 participants have on-treatment HDV RNA continuous decline at least at the last 2 timepoints)

Step 1 – When the first 8 participants randomized to Arm 1 have at least 8 weeks of data assess the antiviral activity criteria a) **and b) and c)**. If criteria a) **and b) and c)** are met, start Part 2. Otherwise, go to Step 2.

Step 2- If the criteria a) **and b) and c)** are not met at Step 1, repeat the review of HDV RNA and HBsAg incremental data available every 2 weeks and make a decision as described in Step 1. If Part 2 has not started by the time 16 participants in Arm 1 have reached Week 36, go to Step 3.

Step 3 – If criteria a) **and b) and c)** have not been met when all 16 participants randomized to active Arm 1 have at least 36 weeks of data, the decision to start Part 2 of the study will be based on the following more detailed rule:

- If 4 or fewer participants out of 16 meet the two criteria a) and b) described above, then Part 2 will not start
- If 5-7 out of 16 participants meet the 2 criteria a) and b) described above, then Part 2 might be started depending on a further review of the individual longitudinal profiles of HDV RNA and HBsAg of all participants. The totality of the HDV RNA and HBsAg data for the participants so far in the study will be taken into account to properly evaluate the magnitude of change and variability over time of the blood markers for each individual.

Step 4 – If Part 2 has not started based on data at Step 3, repeat the review of HDV RNA and HBsAg incremental data available every 2 weeks and make a decision following the rule described in Step 3. If the detailed rule described in Step 3 has not been met by the time when 16 participants randomized to active Arm 1 have at least 44 weeks of data, the study will be stopped for futility.

The antiviral activity criteria become the futility criteria if the antiviral activity is not observed by Week 44 in the 16 participants randomized to JNJ-3989+NA in Part 1. It is worth noting that if the treatment appears ineffective, the futility is declared to avoid that up to 20 participants will be treated for much longer than 1 year.

Since the data for Part 1 and Part 2 are analyzed separately there will be no penalty on the alpha level of one-sided 0.025, used in the efficacy comparisons as described in the rest of this document.

If Part 2 of the study begins, the SC will stop reviewing any Part 2 data and remain blinded to any Part 2 data for the rest of the study up to the time of the primary analysis (see Section 5.2). However, the IDMC will continue monitoring the efficacy data, as well as safety, for both the first 20 subjects randomized in Part 1 and the accruing participants in Part 2. The IDMC will start their review of the HDV and HBV markers 12 weeks after opening of Part 2. This is to ensure the well-being of all participants and avoid HDV RNA rebound/ or unexpected absence/insufficient efficacy trends in terms of HDV RNA/HBsAg declines after Part 2 has been opened and more data will be available. The primary efficacy endpoint will not be reviewed by the IDMC.

Details on the operating characteristics of the antiviral activity criteria to start Part 2 and futility rule are presented in 0.

4. SUBJECT INFORMATION

All the summaries will be done on the ITT analysis set unless specified otherwise. Subject information analyses will be reported by study Parts 1 and 2, as well as for the whole study overall.

4.1. Disposition Information

The number and percentage of participants who are screened, screened failure and reason for that screening failure will be tabulated. Only an all participants group (total N) will be provided.

A summary of the number of participants randomized, randomized and not treated, in the safety, ITT, and mITT sets, respectively, will be summarized by intervention arm. Summaries will be repeated also by DB, OL and FU study phase.

Completion/withdrawal information, study disposition and treatment disposition will be summarized for the ITT, mITT and safety sets (only for ITT and mITT sets if the safety set is identical to ITT).

An overview of the study disposition will be provided by intervention arm and overall. The number and percentage of participants who completed or discontinued (or are ongoing [except the final analysis]) and the number and percentage of participants for each study discontinuation reason will be summarized. The number and percentage of participants under each phase (i.e. double-blind/open-label study intervention phase, follow-up phase) will also be tabulated.

An overview of the treatment disposition will be provided. The number and percentage of participants who completed or discontinued study treatment or were ongoing at the time of the data reviews or IAs cutoff (except the final analysis) will be presented by treatment and intervention arm and phase. The incidences of treatment discontinuation reasons will also be summarized by study intervention arm for each treatment and overall and by phase.

A listing including information (i.e. the date of last study visit, the last study phase and time point [phase and week], the date of discontinuation and the reason) on participants which prematurely discontinue from the study and/or study treatment will be included. Information on the NA treatment, discontinuation and/or re-treatment will also be included.

4.2. Demographic and Baseline Characteristics

Tabulations of demographic and baseline characteristics will be presented by intervention arm and overall for the ITT and mITT analysis sets. Continuous variables will be summarized by descriptive statistics including the number of participants, mean, standard deviation, median and range. Categorical/binary variables will be summarized by counts and percentages.

Additional summaries will be presented by the 3 randomization stratification factors (by presence of compensated cirrhosis at screening, and HDV RNA testing laboratory location, and HBeAg status at screening. The randomization stratification factors are reported by IWRS and also entered in the Electronic Case Report Form (eCRF). A cross-tabulation of the stratification factors collected by the IWRS vs. eCRF will also be provided by intervention arm to identify any mismatch. In case of discrepancies between the 2 sources, the randomization factors as entered in

the eCRF will be used in the analyses/summaries. If the eCRF data is missing, then the IWRS data will be used.

4.2.1. Baseline Characteristics

For the viral activity parameters (e.g. HDV RNA, HBeAg, HBsAg, HBV DNA, HBV RNA, HBcrAg, anti-HBs antibody, anti-HBe antibody), baseline values are used unless specified differently.

- Duration of HBV infection (Years) = (date of randomization – date of HBV infection +1)/365.25; rounded to 1 decimal
- Time since HBV diagnosis (Years) = (date of randomization – date of HBV diagnosis+1)/365.25; rounded to 1 decimal
- Mode of HBV infection: Sexual transmission, intravenously injectable drug use, blood transfusion, hemophilia-associated injection, occupational exposure, mother to child transmission, unknown and other.
- Duration of HDV infection (Years) = (date of randomization – date of HDV infection +1)/365.25; rounded to 1 decimal
- Time since HDV diagnosis (Years) = (date of randomization – date of HDV diagnosis+1)/365.25; rounded to 1 decimal
- Mode of HDV infection: co-infection, super-infection, Other, Unknown.
- Presence of compensated cirrhosis at screening: Yes, No
- Has never received HBV treatment (only for currently not treated participants): Yes, No
- Type of NA at baseline: TeD, TAF, ETV, None
- NA Treatment history at screening:
 - Yes
 - No
- Duration of NA at baseline (Years) = (Sum of all NA treatment duration [prior to randomization])/365.25; rounded to 1 decimal; calculated as: end date – start date +1. If for the latest NA treatment an end date is missing, randomization date is used.
- HDV RNA at baseline (quantitative: IU/mL and log₁₀ IU/mL)
- HDV RNA category at baseline:
 - Participants with HDV RNA < LLOQ
 - Participants with HDV RNA < LLOQ TND
 - Participants with HDV RNA < LLOQ TD
 - Participants with HDV RNA < 500 IU /mL
 - Participants with HDV RNA ≥ 500 IU /mL
 - Participants with HDV RNA < 10000 IU/mL

-
- Participants with HDV RNA > 10000 IU/mL and <100000 IU/mL
 - Participants with HDV RNA \geq 100000 IU/mL
 - Liver Stiffness Measurement (LSM) at baseline (quantitative)
 - LSM category at baseline: 2 kPa - < 7.1 kPa, \geq 7.1 kPa - < 9.5 kPa, \geq 9.5 kPa - < 12.5 kPa, \geq 12.5 kPa
 - HBeAg status at screening: positive, negative
 - HBeAg at baseline (quantitative): values in IU/mL and \log_{10} IU/mL (for HBeAg positive participants only)
 - HBsAg at baseline (quantitative): values in IU/mL and \log_{10} IU/mL
 - HBsAg category at baseline (quantitative: IU/mL):
 - Participants with HBsAg <500 IU/mL
 - Participants with HBsAg <1,000 IU/mL
 - Participants with HBsAg <10,000 IU/mL
 - Participants with HBsAg \geq 10,000 IU/mL
 - HBV DNA at baseline (quantitative): values in IU/mL and \log_{10} IU/mL
 - HBV DNA category at baseline (quantitative: IU/mL):
 - Participants with HBV DNA < LLOQ (20 IU/mL or 10 IU/mL for the new assay)
 - Participants with HBV DNA < 60 IU/mL
 - Participants with HBV DNA < 2,000 IU/mL
 - Participants with HBV DNA < 20,000 IU/mL
 - Participants with HBV DNA \geq 20,000 IU/mL
 - HBV RNA (quantitative): values in copies/mL and \log_{10} copies/mL
 - HBV RNA category at baseline (quantitative: copies/mL):
 - Participants with HBV RNA < LOD
 - Participants with HBV RNA < LLOQ
 - Participants with HBV RNA \geq LLOQ
 - Hepatitis B core related antigen (HBcrAg) at baseline (quantitative): values in \log_{10} U/mL
 - HBcrAg category at baseline (quantitative: \log_{10} U/mL):
 - Participants with HBcrAg <3 \log_{10} U/mL
 - Participants with HBcrAg \geq 3 \log_{10} U/mL-<4 \log_{10} U/mL
 - Participants with HBcrAg \geq 4 \log_{10} U/mL
 - HBsAg Antibody (Anti-HBs) category at baseline (quantitative: mIU/mL):
 - Participants with Anti-HBs <10 mIU/mL
-

- Participants with Anti-HBs \geq 10 mIU/mL
- HBeAg Antibody (Anti-HBe) status at baseline (qualitative): Positive, Negative, Borderline
- Anti-HDV status at baseline: Positive, Negative
- Alanine aminotransferase (ALT) at baseline:
 - Baseline ALT values (U/L)
 - Baseline ALT toxicity grade according to DAIDS
 - Baseline ALT categorization ($\leq 1.0 \times \text{ULN}$, $> 1.0 \times \text{ULN}$ to $< 2.5 \times \text{ULN}$, $\geq 2.5 \times \text{ULN}$)
- Stage of liver fibrosis: F0, F1, F3 or F4
- HBV genotype (using the INNO-LiPA or sequence based HBV genotyping data): Genotype A, B, C, D, E, F, G, H, I, J and Unknown

4.2.2. Demographic Characteristics

The following demographic characteristics will be summarized by study intervention arm and overall.

- Sex: Male, Female
- Age (years)
- Age categories: 18 years - ≤ 30 years, > 30 years - ≤ 45 years, > 45 years - ≤ 60 years, > 60 years
- Race: American Indian or Alaska Native, Asian (Japanese, Other Asian), Black or African American, Native Hawaiian or Other Pacific Islander, White, Not reported, Unknown
 - In case the participant is Asian provide subgroup: Asian Indian, Chinese, Filipino, Japanese, Korean, Vietnamese, Other Asian
- Ethnicity: Hispanic or Latino, Not Hispanic or Latino, Not Reported, Unknown
- Region: Asia (China, Japan, and Other Asian Country), Europe, North America, South America
- Height at baseline (cm)
- Weight at baseline (kg)
- Body mass index (BMI) at baseline (kg/m^2) = weight at baseline (kg) / (height at baseline (m))² (rounded to 1 decimal)
- Body mass index group: Underweight < 18.5 , Normal ≥ 18.5 - < 25 , Overweight ≥ 25 - < 30 and Obese ≥ 30
- History of Tobacco use: Yes/No
- Type of Substance (Beer, Wine, Distilled Spirits): Current/Former/Never
- Type of Substance (Beer, Wine, Distilled Spirits) Duration (Months) = (stop date – start date +1)/30.4375; rounded to 1 decimal

4.3. Medical History

A tabulation of the general medical history coded terms will be provided by body system class and by intervention arm.

4.4. Prior and Concomitant Medications

All medications will be coded using the World Health Organization-Drug Dictionary. Tabulations will include prior and concomitant medications which are defined as follows:

- (i) Prior medications are defined as medications with a start date occurring before the date of DB Day 1 regardless of when dosing of the medication ended.
- (ii) Concomitant medications are defined as medications received on or after Day 1, medication that was received before initial dosing and continued after initial dosing of the study interventions, or medication with missing stop date.

Medication that started before the Day 1 and continued afterwards will be summarized both as prior and, separately, as concomitant medication. All concomitant medications will be allocated to one or multiple analysis phases depending on their start date and end date and also taking into account the eCRF flag to indicate if it is taken before/after study start or still ongoing.

A frequency tabulation of prior medications, and concomitant medications will be shown by Anatomical Therapeutic Chemical (ATC) class level 2, level 4 and preferred terms by intervention arm. In addition, the concomitant medications will be summarized by analysis phase. A listing of prior medications and concomitant medications respectively, will be also provided.

4.5. Protocol Deviations

Major protocol deviations will be based on clinical review, but not limited to, the following criteria: (1) entered but did not satisfy inclusion/exclusion criteria, (2) received wrong treatment or incorrect dose, (3) received a disallowed concomitant treatment, (4) developed withdrawal criteria but not withdrawn, (5) other. Protocol deviations will be closely monitored during the execution of the study and the final set of protocol deviation criteria will be finalized before the primary analysis database lock.

All major protocol deviations will be tabulated by coded term by intervention arm for the ITT analysis set. A listing of the major protocol deviations will be also presented.

In addition, the use of the mITT analysis set in the efficacy analyses will be determined based on the impact of the COVID-19 or similar pandemics prior to database lock for the first IA (i.e. IA during the DB intervention phase for sample size re-estimation). The number and percentage of participants in ITT vs mITT will be summarized by intervention arm.

4.6. Extent of Exposure

Extent of exposure to study treatments will be summarized and presented based on the safety analysis set. The total duration of exposure during the DB and OL study intervention phases will

be calculated by each study treatment (JNJ-3989/placebo and NA) separately and summarized descriptively by intervention arm. The duration of treatment with NA will be summarized also for the follow up phase for participants with presence of compensated cirrhosis at screening by intervention arm.

Because of the different route and frequency of treatment administration across the 2 study treatments (for JNJ-3989/placebo one subcutaneous injection once every 4 weeks, and for NA once daily tablet), the total duration of exposure (weeks) will be calculated by analysis phase for each agent as follows:

- For the DB study intervention phase:
 - JNJ-3989/placebo: $[\text{Min} ((\text{Date of last injection in the DB intervention phase} + 27 \text{ days}), \text{Early study withdrawal visit date, cut-off date}) - \text{date of first injection in the DB phase} + 1] / 7$
 - NA: $[\text{Min} (\text{Date of the last NA administration in the DB phase, Date of discontinuation from NA, Early study withdrawal visit date, cut-off date}) - \text{first drug administration date in the DB phase} + 1] / 7$
- For the OL study intervention phase (only for participants with non-missing OL phase start date, as defined in Section 2.1.1):
 - JNJ-3989: $[\text{Min} ((\text{Date of last injection in the OL phase} + 27 \text{ days}), \text{Early study withdrawal visit date, cut-off date}) - \text{Week 52 study agent intake date} + 1] / 7$
 - NA: $[\text{Min} (\text{Date of the last NA administration in the OL phase, Date of discontinuation from NA, Early study withdrawal visit date, cut-off date}) - \text{Week 52 NA intake date} + 1] / 7$

Cutoff dates will be defined to match the prespecified timepoints for IDMC periodical data reviews, interim analyses and the primary and final analyses, respectively (see Section 3.3).

The number and percentage of participants who skipped any dose of JNJ-3989/placebo or NA will be summarized separately for each study treatment by intervention arm during the DB and OL study intervention phases, separately. Additionally, the number and percentage of participants who missed 2 or more consecutive JNJ-3989/placebo injections, or who missed more than 5 doses of NA within a four-week period will be presented.

For NA treatment, the total duration of exposure will be calculated separately for the DB, OL and FU study phases.

- For the FU study phase:
 - NA: $[\text{Min} (\text{Date of the last NA administration in the FU study phase, Date of discontinuation from NA, Date of trial disposition, Date of clinical cut-off}) - \text{first drug administration date in the FU phase} + 1] / 7$

Those participants who stopped NA treatment at Week 144/Week 148 and never restarted NA treatment thereafter will be counted as having zero weeks of NA exposure during the FU study phase.

4.7. Treatment Compliance

Treatment compliance will be summarized for the safety analysis set by intervention arm for each study treatment except NA.

DB Treatment compliance (%) is defined as follows.

For JNJ-3989/placebo: (Total number of injections received/ 13) * 100%

OL Treatment compliance (%) is defined as follows.

For JNJ-3989 in Arm 1: (Total number of injections received/ 23) * 100%

For JNJ-3989 in Arm 2: (Total number of injections received/ 24) * 100%

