1.2. Trial Design

Prior Protocol Amendment #4 the study was planned to include 2 parts, Part 1 (approximately N=20) with proof of concept objectives and Part 2 (approximately N=145) with confirmatory objectives. As of Protocol Amendment #4, Part 2 sample size was reduced to 30 participants which triggered modifications of objectives of Part 2 from confirmatory to exploratory.

Part 2 of the study will only be initiated once the antiviral activity criteria in Part 1 have been met and after evaluation of the results of the first IA during the double-blind phase of Part 1. Cirrhotic participants will be excluded from participation in Part 2 of the study.

Each part includes 3 phases: a 4-week screening phase (may be extended up to a maximum of 6 weeks), 144-weeks study intervention phase (Arm 1) and 148-weeks study intervention phase (Arm 2), 48-week follow-up phase. The first 52 weeks of the intervention phase are double-blind followed by 96 weeks of open-label (OL) treatment.

In each part the participants will be randomized in a 4:1 ratio to Arms 1:2.

- Arm 1: 100 mg JNJ-3989 (subcutaneous [SC] injection every 4 weeks [Q4W]) + NA qd for 144 weeks;
- Arm 2: placebo for JNJ-3989 (SC injection Q4W) + NA qd for 52 weeks, followed by 100 mg JNJ-3989 (SC injection Q4W) + NA qd for 96 weeks (control deferred active treatment arm).

Randomization will be stratified by presence of compensated cirrhosis at screening (yes or no) (Part 1 only), HDV RNA testing laboratory location (China versus outside China) (all sites in China will utilize the laboratory testing in China and all sites in other countries will utilize the laboratory outside of China), and HBeAg status at screening (positive versus negative).

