3.3.1. Data Reviews

The IDMC will periodically review unblinded cumulative safety and efficacy data at the following timepoints:

Reviews by the IDMC before Part 2 has started (up to approximately 20 participants randomized into the study)

- The first data review (DR) will be performed after approximately 8 participants completed 8 weeks of treatment.
- Thereafter, data reviews will occur approximately every 4 weeks.

Reviews by the Sponsor Committee and selected Study Team members before Part 2 has started

It is worth noting that during this period, the SC will perform every 2 weeks an unblinded review of accruing HDV RNA and HBsAg data to assess the antiviral activity based on criteria defined in Section 3.3.3.

Due to the higher than expected rate of ALT elevations observed among several participants randomized in Part 1, even if the antiviral activity criteria are met, the Sponsor Committee will not initiate Part 2 yet, and continue to review the Part 1 data (see Section 3.3.2.1.1). The Sponsor Committee will make the decision to start Part 2 based on data from or after Part 1 IA1, jointly with the IDMC and unblinded Study team members, based on the preliminary evaluation of the benefit/risk ratio of the investigational treatment regimen.

For safety-related decisions and participant's safety management, selected unblinded data (e.g. HDV RNA and hepatitis B surface antigen [HBsAg]) and treatment assignment will be available to selected team members to instruct the sites to discontinue study treatment in patients receiving active treatment and meeting the additional discontinuation criteria defined in the Protocol Amendment #2.

Reviews by the IDMC after Part 2 has started (enrollment extended beyond the first approximately 20 participants)

- The first data review will be performed after approximately 12 weeks since the start of Part 2 (enrollment expanded to >20 participants).
- Data reviews will occur approximately every 8 weeks up until decision in Protocol Amendment #4 to stop the enrollment.
- Thereafter, data reviews will occur approximately quarterly.

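### Section 4.7 divides injections received by a fixed full-course count for everyone, so the compliance percentage mixes finishing the course with taking the doses that were due (minor; one descriptive table)

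*SAP*

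**What the plan says.** Section 4.7 sets the population first: "Treatment compliance will be summarized for the safety analysis set by intervention arm for each study treatment except NA". Three ratios follow.

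- DB, both arms: "For JNJ-3989/placebo: (Total number of injections received/ 13) * 100".
- OL, Arm 1: "For JNJ-3989 in Arm 1: (Total number of injections received/ 23) * 100".
- OL, Arm 2: "For JNJ-3989 in Arm 2: (Total number of injections received/ 24) * 100".

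The section contains nothing else. It has no term for stopping, withdrawal or a cut-off, no restriction to those who entered the OL phase, and no threshold that separates compliant from non-compliant.

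Section 4.6, immediately before it, works differently. Injection exposure runs to the earliest of the last injection plus 27 days, the early withdrawal visit and the cut-off date, and "Cutoff dates will be defined to match the prespecified timepoints for IDMC periodical data reviews, interim analyses and the primary and final analyses, respectively". OL exposure is calculated only for participants who have an OL start date.

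Two other places bear on who stops or never starts. Section 3.3.1, on reviews before Part 2 opened, provides for sites to be told to "discontinue study treatment in patients receiving active treatment and meeting the additional discontinuation criteria". Section 1.5 and the rationale for SAP Amendment 5 say that Part 2 placebo participants with HBsAg above 10,000 IU/mL at screening or baseline do not receive OL study intervention.

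**The concern.** A compliance percentage is normally read as the share of due doses that were taken. The ratio here answers another question: what share of a completer's course did the participant receive? The two agree only for participants who remain on study agent to the end of the phase.

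They differ in three groups: participants whose study agent was stopped before the phase ended, participants who never started OL dosing, and, for the OL phase, participants still being dosed when data are cut. For these groups a low figure need not mean that any injection was missed. The table cannot tell a directed stop from poor adherence, although the estimands and Attachment 1 treat treatment discontinuation and missed injections as separate intercurrent events. A reader of the compliance table alone could take a low figure as evidence of missed injections.

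**Working it through.** **Inputs.** Section 1.2 gives injections every 4 weeks; Arm 1 receives "100 mg JNJ-3989 (subcutaneous [SC] injection every 4 weeks [Q4W]) + NA qd for 144 weeks". It also states "The first 52 weeks of the intervention phase are double-blind followed by 96 weeks of open-label (OL) treatment". Allocation is 4:1, and Part 2 has 30 participants. The divisors come from Section 4.7.

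**Step 1: reproduce the divisors.**

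- DB, Weeks 0 to 48: 48/4 + 1 = 13.
- OL Arm 1, Weeks 52 to 140: (140 − 52)/4 + 1 = 23. Check: 13 + 23 = 36 = 144/4.
- OL Arm 2, Weeks 52 to 144: (144 − 52)/4 + 1 = 24 = 96/4.

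All three match the SAP. They are full-schedule counts.

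**Step 2: a participant who misses no dose while on treatment.** The score as written is injections received divided by the fixed divisor. The score on doses due is 100% in every row.

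| Last injection given | Received | As written |
|---|---|---|
| DB Week 16 | 5 | 5/13 = 38.5% |
| DB Week 24 | 7 | 7/13 = 53.8% |
| DB Week 36 | 10 | 10/13 = 76.9% |
| OL Week 96, Arm 1 | 12 | 12/23 = 52.2% |
| OL Week 96, Arm 2 | 12 | 12/24 = 50.0% |

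A participant who stays on treatment throughout the DB phase and misses 8 of 13 injections also scores 5/13 = 38.5%.

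**Step 3: effect on an arm mean.** The SAP gives no discontinuation rate, so the share *s* of an arm stopping after the Week 16 injection is an assumption. Everyone else is taken to receive all 13. Mean = 100 × [(1 − s) + s × 5/13].

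| s | Mean DB compliance as written |
|---|---|
| 10% | 93.8% |
| 20% | 87.7% |
| 30% | 81.5% |
| 50% | 69.2% |

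No due dose is missed in any of these rows.

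**Step 4: participants who never start OL dosing.** A Part 2 placebo participant who does not roll over is in the safety set and received no OL injection, so the formula gives 0/24. Expected Part 2 Arm 2 size is 30 × 1/5 = 6. If *k* of the 6 are in this position (assumption) and the rest receive all 24, mean OL compliance is (6 − k)/6: 83.3% for k = 1, 66.7% for k = 2 and 50.0% for k = 3. Read the same way, an Arm 1 participant whose study agent ended in the DB phase would score 0/23 in the OL phase.

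**Step 5: data cuts.** At the primary analysis (Section 5.2) everyone has reached Week 48 or discontinued, so the cut can cost at most the Week 48 injection: 12/13 = 92.3%. By the end-of-OL interim (Section 3.3.2.2) and the final analysis, everyone has finished or stopped OL treatment. A cut therefore matters for OL compliance only if it is tabulated before the end of the OL phase. Table 3 lists extent of exposure at the reviews and interims but does not list compliance.

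**The case against.** The strongest reply is that nothing depends on this percentage and that the facts needed to interpret it are reported elsewhere. Section 4.6 tabulates, by arm and separately for DB and OL, participants who skipped any injection and those who missed two or more in a row. Section 4.1 reports treatment discontinuation with reasons by arm and phase, and lists individual cases. The primary estimand counts discontinuation before Week 48 as non-response. Compliance enters no efficacy model, analysis set or intercurrent event; Attachment 1 counts missed injections directly. The fixed-divisor ratio is also a legitimate measure of course completion. All of this stands, and it keeps the point minor. It does not correct the figure printed under the name of compliance.

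A reader might infer two stronger things, and the SAP supports neither.

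- *That stopped participants are classed as non-compliant.* Section 4.7 has no threshold or category, so they receive a low percentage and no label.
- *That JNJ-3989 will look worse than placebo.* The instruction to stop active-arm participants in Section 3.3.1 sits under reviews before Part 2 opened, so it can lower Arm 1 in the DB phase of Part 1. It cannot be carried to Part 2, where sponsor personnel remain blinded during the DB phase. The roll-over exclusion pulls the other way, lowering Arm 2 in the OL phase, and data cuts affect both arms. Without discontinuation rates by arm, no overall direction can be claimed.

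**Conclusion.** The divisors are correct as full-course counts, but Section 4.7 applies them to participants for whom the full course was never due. Followed exactly, it gives 38.5% to someone who took every injection through Week 16 and was then stopped, and 0/24 to Part 2 placebo participants who were never scheduled for OL injections. The arm-level effect is a mean DB figure of 93.8% to 69.2% with no missed dose. That range rests on the assumption that 10% to 50% of an arm stop after Week 16 and the remainder take all 13. The OL effect in Arm 2 depends on how many of about 6 participants do not roll over.

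Severity is minor: one descriptive table is affected, and no efficacy result changes.

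**What to change.** Rewrite Section 4.7 in three parts.

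1. In each phase, define compliance as injections received in that phase divided by injections scheduled for that participant from phase start to the earliest of permanent study-agent discontinuation, study withdrawal, phase end and cut-off date.
2. Restrict OL compliance to participants who entered OL dosing, following the intent of Section 4.6. State the restriction in terms of dosing: Table 1 sets the OL start date from a projected or actual Week 52 visit, which may not by itself exclude someone who did not roll over.
3. If the course-completion figure is wanted, keep received/13, /23 and /24 as a separate line labelled percent of planned full course.

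The cost is a few lines of SAP wording and a derived count of scheduled injections per participant. No new data are needed and no treatment rule changes.
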